### **7.7.4 Other Analyses**

Summary statistical analyses will be provided for patient disposition, demographics, medical history, physical examination, and concomitant medications.

## **7.8 Data Quality Assurance**

Standard operating procedures are available for all activities performed at the study sites relevant to the quality of this study. Designated study site personnel will be responsible for maintaining quality assurance and quality control to ensure that the study conduct as well as data collection and documentation are performed in compliance with the study protocol, GCP, and Good Laboratory Practice requirements, and applicable regulatory requirements.

All clinical data will undergo a 100% quality control check prior to clinical database lock. Edit checks are then performed for appropriate databases as a validation routine using SAS® to check for missing data, data inconsistencies, data ranges, etc. Corrections are made prior to statistical database lock.

Electronic CRFs can be printed directly from the database. Each eCRF will be reviewed and signed by the Investigator.

## **7.8.1 Data Management**

As part of the responsibilities assumed by participating in the study, the Investigator agrees to maintain adequate case histories for the patients treated as part of the research under this protocol. The Investigator agrees to maintain accurate eCRFs and source documentation as part of the case histories. These source documents may include laboratory reports, ECGs, etc.

Investigative site personnel will enter patient data into eCRFs using the Oracle Clinical Remote Data Capture program. The analysis data sets will be a combination of these data and data from other sources (eg, laboratory data) and follow Clinical Data Interchange Standards Consortium (CDISC) standard.

Clinical data management will be performed in accordance with applicable KBP Biosciences Co., Ltd. standards and data cleaning procedures to ensure the integrity of the data, eg, removing errors and inconsistencies in the data. Adverse events and concomitant medication terms will be coded using the MedDRA and World Health Organization Drug Dictionaries, respectively.

After database lock, each study site will receive a CD-ROM containing all site-specific eCRF data as entered into Oracle Clinical Remote Data Capture for the study, including full discrepancy and audit history. Additionally, a CD-ROM copy of all of the study site's data from the study will be created and sent to the Sponsor for storage. DaVita Clinical Research will maintain a duplicate CD-ROM copy for their records. In all cases, patient initials will not be collected or transmitted to the Sponsor.

## **8 Ethics**

### **8.1 Institutional Review Board**

Federal regulations and the ICH guidelines require that approval be obtained from an Institutional Review Board (IRB) before participation of human patients in research studies. Before study onset, the protocol, informed consent, advertisements to be used for the recruitment of study patients, and any other written information regarding this study to be provided to the patient or the patient's legal guardian must be approved by the IRB. Documentation of all IRB approvals and of the IRB compliance with ICH harmonised tripartite guideline E6 (R1): GCP will be maintained by the site and will be available for review by the Sponsor or its designee.

All IRB approvals should be signed by the IRB chairman or designee and must identify the IRB name and address, the clinical protocol by title or protocol number or both, and the date approval or a favorable opinion was granted.

The Investigator is responsible for providing written summaries of the progress and status of the study at intervals not exceeding 1 year or otherwise specified by the IRB. The Investigator must promptly supply the Sponsor or its designee, the IRB, and, where applicable, the institution, with written reports on any changes significantly affecting the conduct of the study or increasing the risk to patients.

## **8.2 Ethical Conduct of the Study**

The study will be performed in accordance with the ethical principles that have their origin in the Declaration of Helsinki, ICH GCP, and all applicable regulations.

## **8.3 Patient Information and Consent**

A written informed consent in compliance with US Title 21 Code of Federal Regulations (CFR) Part 50 shall be obtained from each patient before entering the study or performing any unusual or non-routine procedure that involves risk to the patient. An informed consent template may be provided by the Sponsor to investigative sites. If any institution-specific modifications to study-related procedures are proposed or made by the site, the consent should be reviewed by the Sponsor or its designee or both before IRB submission. Once reviewed, the consent will be submitted by the Investigator to his or her IRB for review and approval before the start of the study. If the ICF is revised during the course of the study, all active participating patients must sign the revised form.

Before recruitment and enrollment, each prospective patient or his or her legal guardian will be given a full explanation of the study and be allowed to read the approved ICF. Once the Investigator is assured that the patient/legal guardian understands the implications of participating in the study, the patient/legal guardian will be asked to give consent to participate in the study by signing the ICF.

The Investigator shall retain the signed original ICF(s) and give a copy of the signed original form to the patient or legal guardian.

## **9 Investigator's Obligations**

The following administrative items are meant to guide the Investigator in the conduct of the study but may be patient to change based on industry and government standard operating procedures, working practice documents, or guidelines. Changes will be reported to the IRB but will not result in protocol amendments.

## **9.1 Confidentiality**

All laboratory specimens, evaluation forms, reports, and other records will be identified in a manner designed to maintain patient confidentiality. All records will be kept in a secure storage area with limited access. Clinical information will not be released without the written permission of the patient (or the patient's legal guardian), except as necessary for monitoring and auditing by the Sponsor, its designee, the Food and Drug Administration (FDA), or the IRB.

The Investigator and all employees and coworkers involved with this study may not disclose or use for any purpose other than performance of the study any data, record, or other unpublished, confidential information disclosed to those individuals for the purpose of the study. Prior written agreement from the Sponsor or its designee must be obtained for the disclosure of any said confidential information to other parties.

## **9.2 Financial Disclosure and Obligations**

Investigators are required to provide financial disclosure information to allow the Sponsor to submit the complete and accurate certification or disclosure statements required under 21 CFR 54. In addition, the Investigator must provide to the Sponsor a commitment to promptly update this information if any relevant changes occur during the course of the investigation and for 1 year following the completion of the study.

Neither the Sponsor nor DaVita Clinical Research is financially responsible for further testing or treatment of any medical condition that may be detected during the screening process. In addition, in the absence of specific arrangements, neither the Sponsor nor DaVita Clinical Research is financially responsible for further treatment of the patient's disease.

## **9.3 Investigator Documentation**

Before beginning the study, the Investigator will be asked to comply with ICH E6 (R1) Section 8.2 and Title 21 of the CFR by providing the following essential documents, including but not limited to:

- IRB approval
- Original signed Investigator agreement page of the protocol
- Form FDA 1572, fully executed, and all updates on a new fully executed Form FDA 1572
- Curriculum vitae for the Investigator and each Sub-Investigator listed on Form FDA 1572

- Financial disclosure information to allow the Sponsor to submit complete and accurate certification or disclosure statements required under 21 CFR 54. In addition, the Investigators must provide to the Sponsor a commitment to promptly update this information if any relevant changes occur during the course of the investigation and for 1 year after the completion of the study.
- IRB-approved informed consent, samples of site advertisements for recruitment for this study, and any other written information regarding this study that is to be provided to the patient or legal guardian, and
- Laboratory certifications and normal ranges for any local laboratories used by the site, in accordance with 42 CFR 493

#### **9.4 Study Conduct**

The Investigator agrees that the study will be conducted according to the principles of ICH E6 (R1). The Investigator will conduct all aspects of this study in accordance with all national, state, and local laws or regulations. Study information from this protocol will be posted on publicly available clinical trial registers before enrollment of patients begins.

#### **9.5 Adherence to Protocol**

The Investigator agrees to conduct the study as outlined in this protocol in accordance with ICH E6 (R1) and all applicable guidelines and regulations.

#### **9.6 Adverse Events and Study Report Requirements**

By participating in this study the Investigator agrees to submit reports of SAEs according to the time line and method outlined in the protocol. In addition, the Investigator agrees to submit annual reports to the study site IRB as appropriate.

#### **9.7 Investigator's Final Report**

Upon completion of the study, the Investigator, where applicable, should inform the institution; the Investigator/institution should provide the IRB with a summary of the study's outcome and the Sponsor and regulatory authority with any reports required.

#### **9.8 Records Retention**

Essential documents should be retained until at least 2 years after the last approval of a marketing application in an ICH region and until there are no pending or contemplated marketing applications in an ICH region, or at least 2 years have elapsed since the formal

discontinuation of clinical development of the study drug. These documents should be retained for a longer period, however, if required by the applicable regulatory requirements or by an agreement with the Sponsor. It is the responsibility of the Sponsor to inform the Investigator/institution as to when these documents no longer need to be retained.

## **9.9 Publications**

After completion of the study, the data may be considered for reporting at a scientific meeting or for publication in a scientific journal. In these cases, the Sponsor will be responsible for these activities and will work with the Investigators to determine how the manuscript is written and edited, the number and order of authors, the publication to which it will be submitted, and other related issues. The Sponsor has final approval authority over all such issues.

Data are the property of the Sponsor and cannot be published without prior authorization from the Sponsor, but data and publication thereof will not be unduly withheld.

## **10 Study Management**

### **10.1 Monitoring**

#### **10.1.1 Monitoring of the Study**

The clinical monitor and/or designee, as a representative of the Sponsor, has the obligation to follow the study closely. In doing so, the monitor will visit the Investigator and study site at periodic intervals, in addition to maintaining necessary telephone and letter contact. The monitor will maintain current personal knowledge of the study through observation, review of study records and source documentation, and discussion of the conduct of the study with the Investigator and personnel.

All aspects of the study will be carefully monitored, by the Sponsor or its designee, for compliance with applicable government regulation with respect to current GCP and current standard operating procedures.

#### **10.1.2 Inspection of Records**

Investigators and institutions involved in the study will permit study-related monitoring, audits, IRB review, and regulatory inspections by providing direct access to all study records. In the event of an audit, the Investigator agrees to allow the Sponsor, representatives of the Sponsor, or a regulatory agency (eg, FDA or other regulatory agency) access to all study records.

The Investigator should promptly notify the Sponsor and DaVita Clinical Research of any audits scheduled by any regulatory authorities and promptly forward copies of any audit reports received to the Sponsor.

## **10.2 Management of Protocol Amendments and Deviations**

### **10.2.1 Modification of the Protocol**

Any changes in this research activity, except those necessary to remove an apparent, immediate hazard to the patient, must be reviewed and approved by the Sponsor or its designee. Amendments to the protocol must be submitted in writing to the Investigator's IRB for approval before patients can be enrolled into an amended protocol, and before the changes can be implemented.

### **10.2.2 Protocol Deviations**

The Investigator or designee must document and explain in the patient's source documentation any deviation from the approved protocol. The Investigator may implement a deviation from, or a change of, the protocol to eliminate an immediate hazard to study patients without prior IRB approval. As soon as possible after such an occurrence, the implemented deviation or change, the reasons for it, and any proposed protocol amendments should be submitted to the IRB for review and approval, to the Sponsor for agreement, and to the regulatory authorities, if required.

A protocol deviation is defined as an unintended or unanticipated departure from the procedures or processes approved by the Sponsor and the IRB and agreed to by the Investigator. A major deviation occurs when there is not adherence to the protocol by the patient or Investigator that results in a significant, additional risk to the patient. Major deviations can include not adhering to inclusion or exclusion criteria, enrollment of the patient without prior Sponsor approval, or not adhering to FDA regulations or ICH GCP guidelines, and will lead to the patient being withdrawn from the study ([Section 4.2](#)).

Protocol deviations will be documented by the clinical monitor throughout the course of monitoring visits. Investigators will be notified in writing by the monitor of deviations. The IRB should be notified of all protocol deviations in a timely manner.

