## **4.2 Withdrawal of Patients from the Study**

The duration of the study is defined for each patient as the date signed written informed consent is provided through the end of study assessment, which will be on Day 14 for Part 1 and Part 2 or the date of Early Termination (ET) for patients who are withdrawn prior to the end of study assessment.

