### **4.2.1 Reasons for Withdrawal/Discontinuation**

Patients may withdraw from the study at any time and for any reason without prejudice to their future medical care by the Investigator or at the study site. Every effort should be made to keep patients in the study. The reasons for patients not completing the study will be recorded. A patient may be withdrawn from the study for any of the following reasons:

1. Does not meet the protocol inclusion or exclusion criteria.
2. Noncompliance with the protocol.
3. A serious or intolerable AE that in the Investigator's opinion requires withdrawal from the study, including but not limited to laboratory safety assessments that reveal CS hematological or biochemical changes from the baseline values and symptoms or an intercurrent illness that justifies withdrawal.
4. Lost to follow-up.
5. Other (eg, pregnancy, development of contraindications of use of study drug).

6. The patient withdraws consent, or the Investigator or Sponsor decide to discontinue the patient's participation in the study.
7. The Investigator will also withdraw a patient if KBP Biosciences Co., Ltd. terminates the study.

Upon occurrence of a serious or intolerable AE, the Investigator will confer with the Sponsor. If a patient is discontinued because of an AE, the event will be followed until it is resolved. Any patient may withdraw his or her consent at any time.

Patient safety will be closely monitored throughout the study and the study will be conducted following GCP. All safety data and any available PK data will be reviewed after each cohort for Part 1 and Part 2 of the study to ensure patient safety. The entire study may be stopped at any time at the discretion of the Investigator in consultation with KBP Biosciences Co., Ltd.

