#### **4.2.2 Handling of Withdrawals**

Patients are free to withdraw from the study or study treatment at any time upon request. Patient participation in the study may be stopped at any time at the discretion of the Investigator or at the request of the Sponsor.

Patients who discontinue study treatment or active participation in the study will no longer receive study drug. When a patient withdraws from the study, the reason(s) for withdrawal shall be recorded by the Investigator on the relevant page of the electronic case report form (eCRF). Whenever possible, all patients who discontinue study treatment or withdraw from the study prematurely will undergo all end-of-study assessments at the time of ET. Patients who fail to return for final assessments will be contacted by the site in an attempt to have them comply with the protocol. Methods for follow up will consist of 2 documented phone calls followed by 1 registered letter.

It is vital to obtain follow-up data on any patient withdrawn because of an AE or serious adverse event (SAE). In every case, efforts must be made to undertake protocol-specified, safety, follow-up procedures.

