### **6.1.6.6 Follow-Up of Patients Reporting Adverse Events**

All AEs must be reported in detail on the appropriate page of the eCRF and followed to satisfactory resolution, until the Investigator deems the event to be chronic or not CS, or until the patient is considered to be stable.

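### Section 10.2.2 makes withdrawal mandatory for a major deviation even after the only dose, while Section 4.2.1 leaves it to judgment; after dosing this cuts scheduled potassium follow-up without reducing exposure

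*Protocol*

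**What the plan says.** Protocol Section 10.2.2 defines a major deviation as nonadherence that puts the patient at significant additional risk. It gives breaches of the inclusion or exclusion criteria as an example and states the consequence: "and will lead to the patient being withdrawn from the study". It refers to Section 4.2 and does not distinguish patients already dosed from those not yet dosed.

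Section 4.2.1, within Section 4.2, is permissive: "A patient may be withdrawn from the study for any of the following reasons". The first reason listed is "Does not meet the protocol inclusion or exclusion criteria" and the second is noncompliance. The same section says "Every effort should be made to keep patients in the study".

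Three provisions govern what follows withdrawal:
- Section 4.2 ends the patient's study at the ET date "for patients who are withdrawn prior to the end of study assessment".
- Section 4.2.2 says that, where possible, patients who "withdraw from the study prematurely will undergo all end-of-study assessments at the time of ET". It adds: "In every case, efforts must be made to undertake protocol-specified, safety, follow-up procedures".
- Section 6.1.6.6 requires adverse events to be "followed to satisfactory resolution, until the Investigator deems the event to be chronic or not CS", or until the patient is stable.

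Section 6.1.5 promises close monitoring of serum potassium throughout the study.

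**The concern.** The two sections give a site different instructions for the same patient. Suppose a breach that adds significant risk comes to light on Day 4. Section 10.2.2 requires withdrawal, and Section 4.2.1 leaves it open.

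The mandatory rule also suits a single-dose study poorly. In a multiple-dose study withdrawal protects the patient by stopping treatment. Here the only dose is given on Day 1, so withdrawal afterwards stops nothing except observation. The rule applies to patients singled out for added risk. The clearest cases concern potassium: a Part 1 patient found after dosing to have had a Check-in value above 4.8 mmol/L (Inclusion Criterion 4), or any patient found to be taking a potassium-sparing diuretic (Exclusion Criterion 23). Such patients have the most reason to complete the scheduled potassium checks.

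**Working it through.** The protocol gives no figure on this point to reproduce. The check sets the texts side by side, then counts what withdrawal would cut.

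**1. Do the rules meet on the same ground?** Section 10.2.2 covers eligibility breaches that add significant risk and makes withdrawal mandatory. Section 4.2.1, item 1, covers all eligibility breaches and makes withdrawal optional. For a breach without significant added risk only Section 4.2.1 applies, and there is no conflict. For a breach with such risk both apply and they differ.

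**2. What does withdrawal after dosing remove?** Sections 5.1 and 5.2 give one 0.5 mg dose on Day 1. Doses left to withhold afterwards: 1 − 1 = 0. Exposure is unchanged.

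**3. What happens to scheduled potassium?** In Table 12-1 the laboratory samples at 24 to 264 h in Part 1 are for creatinine only. Scheduled outpatient potassium before Day 14 therefore comes only from the biomarker samples, at 2, 6, 12, 24, 48, 72, 96, 120, 168, 216, 264 and 312 h (12 postdose times; the Part 2 footnote lists the same times). Samples still to come after withdrawal at time *w* are those with time > *w*:

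| Withdrawal just after | Still to come | Share of 12 |
|---|---|---|
| 24 h | 8 | 67% |
| 48 h | 7 | 58% |
| 72 h | 6 (96, 120, 168, 216, 264, 312 h) | 50% |
| 120 h | 4 (168, 216, 264, 312 h) | 33% |

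If the ET set is obtained it returns one time point. After 72 h, 6 scheduled times become 1, a net loss of 5.

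**4. Is drug still present?** Section 1.3 gives an average half-life in healthy subjects of more than 50 h. Assume 50 to 65 h and mono-exponential decline after 24 h. The concentration at time *T* relative to 24 h is 2^(−(T−24)/h):
- 72 h: 2^(−48/50) = 0.51; 2^(−48/65) = 0.60.
- 120 h: 2^(−96/50) = 0.26; 2^(−96/65) = 0.36.

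Substantial drug remains over the days at issue. This shows presence, not hazard.

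**5. How large is the PK loss?** After 72 h, 6 of the 16 postdose PK samples in Part 1 are still to come. Section 1.3 gives healthy-subject AUCs at 0.5 mg of 162.5 (0–24 h) and 678.4 ng·h/mL (to infinity), so the share after 24 h is (678.4 − 162.5)/678.4 = 0.76. Under the assumptions in step 4, the extrapolated share of AUC0-∞ with the last sample at *T* is 0.76 × 2^(−(T−24)/h). With ET assumed at 96 h this is 28% to 35%, against 1.4% to 3.5% at 312 h. Cmax, tmax and AUC0-24h are unaffected. One event touches one profile of 6 (17%), and Sections 3.1 and 4.2.3 allow replacement.

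**The case against.** The two sections can largely be read together: Section 4.2.1 is a general list, and Section 10.2.2 hardens it only for breaches with significant added risk. Section 4.2.1 does not use its verbs strictly either, since its item 7 uses *will* under a heading that says *may*. Its sentence on keeping patients follows one on voluntary withdrawal, so it is weak evidence against removal by the sponsor or investigator. All this stands. It narrows the conflict to high-risk eligibility breaches but does not remove it there.

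A reader might infer that withdrawal ends potassium checks altogether. The documents do not support that. The ET set includes chemistry and a biomarker sample. Section 4.2.2 calls for efforts at safety follow-up, although that sentence follows one about withdrawals for adverse events, so its reach is uncertain. Section 6.1 allows extra assessments at the investigator's discretion, Section 6.1.5 requires a repeat of potassium above 5.6 mmol/L, and adverse events are followed up. None of these, however, restores the scheduled series to Day 14.

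A reader might also infer that patients would be harmed. That is not shown. The dose is the lowest tested in humans, and 46 healthy subjects given up to 30 mg showed no clinically meaningful potassium trend. The warning about potassium-sparing diuretics in Section 1.1 concerns eplerenone. Healthy subjects are not patients with severe kidney disease, but presence of drug alone does not establish risk.

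Late discovery is also guarded against: potassium is tested locally for speed, and eligibility and previous medications are reviewed again on Day −1. Finally, mandatory withdrawal for serious breaches is a choice a sponsor can defend. That is strongest where consent is invalid or procedures are unsafe, and the fix keeps both cases out.

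**Conclusion.** The point holds in a limited form. For an eligibility breach with significant added risk, Section 10.2.2 requires what Section 4.2.1 leaves to judgment, and it makes no exception after the only dose. Withdrawal then gains nothing in exposure and replaces the remaining scheduled potassium samples with one ET set, where possible, and follow-up of unclear scope.

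The sample counts come directly from the schedule, but the withdrawal times are illustrative. The figures for remaining drug and extrapolated AUC also depend on an assumed half-life of 50 to 65 h, healthy-subject data and, for the AUC, an assumed ET time; values in these patients are not given. The documents give no event rate, and the number may be zero. Discovery before dosing, or late in follow-up, costs little or nothing. PK loss is secondary and replaceable; the withdrawn patient's own safety follow-up is not. Importance is low to moderate, and the case for changing the text rests largely on how little the change costs.

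**What to change.** In Section 10.2.2, replace the mandatory wording so that a major deviation *may* lead to withdrawal under Section 4.2.1. Then add:

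- A patient found ineligible before dosing is not dosed.
- A patient already dosed continues scheduled safety assessments, including potassium, and PK assessments to Day 14, unless consent is withdrawn or was not validly obtained, or the investigator judges continued procedures unsafe.
- Membership of the PK Population is decided separately under Section 7.5.

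The cost is one or two sentences in an amendment. The drawback is that some profiles will carry a deviation flag, and their use in the PK summaries will have to be decided case by case.
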